## 8.1.8 Administration

Ipilimumab is to be administered as a 90-minute infusion. When both study drugs are to be administered on the same day, separate infusion bags and filters must be used for each infusion. Nivolumab is to be administered first. The nivolumab infusion must be promptly followed by a saline flush to clear the line of nivolumab before starting the ipilimumab infusion. The second infusion will always be ipilimumab and will start no sooner than 30 minutes after completion of the nivolumab infusion.

## 8.1.9 Ordering

Ipilimumab will be supplied by BMS. No patients or third-party payers will be charged. Use the Drug Supply Request Form provided to order ipilimumab. For all inquiries regarding ipilimumab supplies, please contact: [contact].

# 8.1.10 Accountability

The investigator, or a responsible party designated by the investigator, will maintain a careful record of the inventory and disposition of ipilimumab using a drug accountability form that is compliant with local and federal guidelines.

Additionally, a designated study team member will complete drug accountability/reconciliation based on the participant actual drug return versus the anticipated drug return and document the findings according to local and federal regulations and guidance.

# 8.1.11 Destruction and Return

After full drug accountability and reconciliation, all unused ipilimumab will be destroyed according to site procedures. Destruction will be documented in the Drug Accountability Record Form. If any study drug is lost or damaged, the disposition of the study drug should be documented.

#### 8.2 Nivolumab

## 8.2.1 Description

Nivolumab is a fully human, IgG4 (kappa) isotype, mAb that binds to PD-1. Following single dose, maximum concentration (Cmax), and area under the curve (AUCinf) of nivolumab were found to be dose proportional within the studied dose range of 0.3-10 mg/kg. The terminal half-life of nivolumab from single dose was 17-25 days in patients with multiple tumor types. Following multiple doses of 0.1 to 10 mg/kg administered every 2 weeks, Cmax and AUC of nivolumab were found dose proportional. The steady-state is expected to be achieved by the sixth dose.

## 8.2.2 Form

Injection: 100 mg/10 mL (5 mg/mL) as a clear, colorless to pale yellow liquid in a single-use vial.

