#### 1. OBJECTIVES

## 1.1 Study Design

This is an open-label phase II study of ipilimumab with or without nivolumab for patients with relapsed or refractory (R/R) classic Hodgkin lymphoma (cHL).

Patients who have previously failed a PD-1 mAb will receive 4 cycles of ipilimumab monotherapy and then undergo a restaging PET scan. Patients achieving an objective response will continue ipilimumab maintenance therapy. Patients with SD or progressive disease (PD) (if clinically stable) will receive 4 cycles of combination therapy with ipilimumab and nivolumab followed by ipilimumab maintenance therapy. Patients who have progressive disease after fewer than 4 cycles of ipilimumab are also eligible to proceed to combination therapy with nivolumab and ipilimumab, if they are clinically stable. The primary endpoint will be objective response rate (ORR) to 4 cycles of ipilimumab monotherapy.

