The frequent expression of CTLA-4 and its ligand CD86 within the cHL TME provide a strong biologic rationale for CTLA-4 directed therapies in cHL. In addition, available clinical data suggests that ipilimumab has clinical activity and a tolerable risk profile when used as monotherapy or in combination with nivolumab. We have designed a phase II trial that targets the use of ipilimumab to those patients who derive less benefit from PD-1 blockade with the goal of limiting overall toxicity exposure. The trial will utilize a response-adapted design among patients who failed PD-1 mAb therapy. Patients will begin with ipilimumab monotherapy and then undergo a restaging PET/CT. Patients achieving an objective response will continue treatment with ipilimumab maintenance, while non-responders will receive ipilimumab and nivolumab re-induction therapy for 4 cycles followed by ipilimumab maintenance treatment. Given the key role of the PD-1 axis, we hypothesize that some patients may benefit from the addition of nivolumab to CTLA-4 blockade even after they have progressed following treatment with both treatments alone. Observation of objective responses to combination therapy with nivolumab and ipilimumab in this setting would provide strong evidence of synergy with combined PD-1 and CTLA-4 blockade.

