#### 5. TREATMENT PLAN

## Figure 1 Trial Schema

Patients with R/R cHL who have previously failed a PD-1 mAb will be enrolled. For details regarding dosing, see section 5.1. Study therapy is expected to be administered on an outpatient basis. Patients will receive 4 doses of ipilimumab therapy dosed every 3 weeks (12 weeks), followed by a restaging PET/CT scan. Patients achieving an objective response to ipilimumab monotherapy will receive up to 8 doses of maintenance ipilimumab dosed every 12 weeks (96 weeks), for a total of 108 weeks of study therapy. Patients with SD or PD following ipilimumab monotherapy (who are clinically stable) will receive 4 cycles of combination ipilimumab and nivolumab therapy dosed every 3 weeks (12 weeks), followed by up to 7 doses of maintenance ipilimumab dosed every 12 weeks (84 weeks), for a total of up to 108 weeks of study therapy. Patients who have progressive disease after fewer than 4 cycles of ipilimumab are eligible to proceed to combination therapy with nivolumab and ipilimumab if they are clinically stable. Therapy will be stopped sooner for unacceptable toxicity, patient withdrawal, disease progression, physician decision, or death. Patients achieving a complete response for ≥ 6 months

can elect to stop study therapy.

Patients will be evaluated with PET/CT scans at baseline and again after 4 doses of ipilimumab monotherapy (week 12) (or earlier if there is clinical concern for progression). Among ipilimumab responders, restaging scans will occur prior to ipilimumab maintenance cycle 2 (week 24), cycle 3 (week 36), cycle 5 (week 60), and cycle 7 (week 84). Among ipilimumab non-responders, restaging scans will occur after 4 cycles of ipilimumab + nivolumab combination therapy (week 24) and prior to ipilimumab maintenance cycle 2 (week 36), cycle 4 (week 60), and cycle 6 (week 84). The end-of-treatment assessment will occur 4-12 weeks after the last doses of study therapy (i.e. weeks 112-120 for patients who complete all planned study therapy). Afterwards, patients will be re-imaged every 24 weeks. Patients in CR at any time point may have CT imaging only at subsequent time points.

Toxicity will be continuously monitored and recorded using CTCAE 5 criteria, up to 30 days following the last dose of the study treatment or until resolution of toxicity to grade 1 or baseline, whichever occurs last.

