#### **5.1** Treatment Regimen

**Table 1 Treatment regimen** 

Induction	Ipilimumab 3 mg/kg	Ipilimumab 3 mg/kg
treatment	every 3 weeks for 4	every 3 weeks for 4
	doses	doses
Re-induction	Ipilimumab responders:	Ipilimumab non-
	Not applicable	responders:
		Nivolumab 3mg/kg +
		Ipilimumab 1 mg/kg
		every 3 weeks for 4
		doses (i.e. on day 1 of
		each 3-week cycle)
Maintenance	Ipilimumab 3 mg/kg	Ipilimumab 3 mg/kg
treatment	every 12 weeks (for up to	every 12 weeks (for up
	8 doses)	to 7 doses)

Patients will receive ipilimumab 3 mg/kg every 3 weeks for 4 doses followed by a restaging PET/CT scan. Patients achieving an objective response to ipilimumab monotherapy will receive up to 8 doses of maintenance ipilimumab dosed at 3mg/kg every 12 weeks (96 weeks), for a total

of 108 weeks of study therapy. Patients with SD or PD after ipilimumab monotherapy, (who are clinically stable) will receive 4 cycles of combination ipilimumab 1 mg/kg and nivolumab 3 mg/kg dosed every 3 weeks (12 weeks), followed by up to 7 doses of maintenance ipilimumab dosed at 3 mg/kg every 12 weeks (96 weeks), for a total of up to 108 weeks of study therapy. Patients who have progressive disease after fewer than 4 cycles of ipilimumab are eligible to proceed to combination therapy with nivolumab and ipilimumab if they are clinically stable. Patients will continue study therapy until PD\* or unacceptable toxicity. Patients achieving a complete response for  $\geq$  6 months can elect to stop ipilimumab therapy.

Patients can opt to continue trial therapy beyond progression if they meet the conditions described in Section 5.6.

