## 5.3 Agent Administration

## 5.3.1 Ipilimumab

Ipilimumab will be administered intravenously as a 90-minute infusion (+/- 15 minutes) on day 1 of each cycle at a dose of 1 mg/kg when administered in combination with nivolumab and at a dose of 3 mg/kg when administered alone. Maintenance ipilimumab (3 mg/kg) will be administered once every 12 weeks. Dosing of ipilimumab will be based on actual body weight. When both study drugs are to be administered on the same day, separate infusion bags and filters must be used for each infusion. Nivolumab is to be administered first. The nivolumab infusion must be promptly followed by a saline flush to clear the line of nivolumab before starting the ipilimumab infusion. The second infusion will always be ipilimumab and will start no sooner than 30 minutes after completion of the nivolumab infusion. For management of infusion reactions, see section 6.6.

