#### 8.1.2 Form

Injection: 50 mg/10 mL (5 mg/mL) as a clear to slightly opalescent, colorless to pale-yellow solution in a single-use vial.

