## 8.2.7 Preparation

Please refer to the current IB/pharmacy reference sheets for preparation instructions. Study product should be prepared and dispensed by an appropriately qualified and experienced member of the study staff (eg, physician, nurse, physician's assistant, practitioner, pharmacist, or medical assistant) as allowed by local, state, and institutional guidance. Only qualified personnel who are familiar with procedures that minimize undue exposure to them and to the environment should undertake the preparation, handling, and safe disposal of biologic agents.

During the first 4 cycles, dosing of nivolumab will be based on the patient's weight in kilograms (kgs), whereas maintenance nivolumab will be administered at a flat dose of 480 mg. All patients should be weighed within 3 days prior to dosing for cycles 1-4 to ensure they did not experience either a weight loss or gain >10% from the weight used for the last dose calculation. If the patient experienced either a weight loss or gain >10% compared to the weight used for the last dose calculation, the amount of study drug must be recalculated.

Vials are for single use only. Any unused portion of the solution must be discarded in a biohazard waste disposal container with final disposal according to accepted local and national standards of incineration.

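### The nivolumab pharmacy text has two errors: 8.2.2 prints 100 mg/10 mL as 5 mg/mL, and 8.2.7 gives a 480 mg maintenance dose that the regimen does not contain

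*Combined protocol and SAP*

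**What the plan says.** **Vial strength.** Section 8.2.2 gives the nivolumab form as "Injection: 100 mg/10 mL (5 mg/mL) as a clear, colorless to pale yellow liquid in a single-use vial". The matching ipilimumab entry in 8.1.2 reads "Injection: 50 mg/10 mL (5 mg/mL) as a clear to slightly opalescent".

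**Maintenance dose.** Section 8.2.7 makes nivolumab weight-based in the opening four cycles and then says "maintenance nivolumab will be administered at a flat dose of 480 mg". The treatment sections describe something else:

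- Section 1.1: patients with stable or progressive disease "will receive 4 cycles of combination therapy with ipilimumab and nivolumab followed by ipilimumab maintenance therapy".
- Section 2.4: "re-induction therapy for 4 cycles followed by ipilimumab maintenance treatment".
- Section 5.1: re-induction is "followed by up to 7 doses of maintenance ipilimumab dosed at 3 mg/kg every 12 weeks", and the maintenance row of Table 1 lists only ipilimumab in both columns.
- Section 5.3.1: "Maintenance ipilimumab (3 mg/kg) will be administered once every 12 weeks".
- Section 5.3.2: the only nivolumab dose is 3 mg/kg.
- Table 7: nivolumab is marked under re-induction cycles 1-4 and nowhere in the maintenance columns.

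**The concern.** Section 8.2.2 offers two strengths for one product, and they cannot both be true. Section 8.2.7 gives a dose for a treatment phase that the rest of the protocol does not have. Both statements sit in the pharmacy section of a multi-center protocol, where external sites store and dispense the drug. A strength that is wrong by a factor of 2 feeds directly into the volume drawn up if anyone relies on it, and a stray flat dose conflicts with the regimen. Statements of this kind should be correct even when other safeguards make harm unlikely.

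**Working it through.** **1. Strength.** Concentration is mass divided by volume.

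- Ipilimumab, 8.1.2: 50 mg / 10 mL = 5 mg/mL. This reproduces the printed figure.
- Nivolumab, 8.2.2: 100 mg / 10 mL = 10 mg/mL. The printed figure is 5 mg/mL, so it is not reproduced. The ratio is 10 / 5 = 2.
- A strength of 5 mg/mL would need 50 mg in 10 mL or 100 mg in 20 mL, and neither is printed for nivolumab.

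The bracket is identical to the one in the ipilimumab entry, so it may have been carried over, but that is an inference. The documents show the contradiction without proving which figure is the slip.

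**2. What a factor of 2 means in volume.** The protocol gives no body weights, so 50 to 100 kg is assumed here for illustration.

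| Weight (assumed) | Dose at 3 mg/kg | Volume at 10 mg/mL | Volume at 5 mg/mL |
|---|---|---|---|
| 50 kg | 150 mg | 15 mL | 30 mL |
| 100 kg | 300 mg | 30 mL | 60 mL |

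This shows the size of the discrepancy. It is not a forecast, since a preparer would have to follow the bracket and ignore the mass and volume printed beside it, the vial and the reference sheets.

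**3. Scheduled nivolumab.** Table 1 and Table 7 give 4 doses per patient who completes re-induction and 0 in maintenance. With the 13 patients planned in 13.2, the ceiling is 13 x 4 = 52 doses. Section 13.3 uses response rates of 10% (null) and 40% (alternative). If every non-responder completed re-induction, the counts would be:

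- 10% response: 13 x 0.9 x 4 = 46.8, about 47 doses
- 40% response: 13 x 0.6 x 4 = 31.2, about 31 doses

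These are upper figures, because re-induction requires clinical stability and therapy can stop early. They count scheduled doses, not errors.

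**4. Could the 480 mg dose belong somewhere else?**

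- Section 2.3.3 mentions flat doses of 240 to 480 mg, but as background pharmacokinetics.
- The nivolumab continuation described in 2.4 belongs to an earlier trial.
- Section 6.7 lets a patient continue one agent after stopping the other, but names neither a 480 mg dose nor a nivolumab maintenance phase.
- Section 5.3.2 refers only to the relevant cycles. It supports 3 mg/kg without itself limiting which cycles.

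None of these supplies a 480 mg regimen. The wording of 8.2.7 misfits the design in a second way: cycles 1-4 are ipilimumab monotherapy, and nivolumab starts only at re-induction.

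**5. Primary test.** Neither statement enters the rule in 13.3. That rule (4 or more responses in 13, null 10%, alternative 40%) gives an exact one-sided error of 0.0342 and power of 0.831, which agree with the stated 0.034 and 0.83.

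**The case against.** The best reply is that this is proofreading. The 8.2.2 line describes a product and gives no dilution instruction, no calculation in the protocol uses 5 mg/mL, and the correct quotient can be read from the same line. Preparation is restricted to qualified staff and referred to the current investigator's brochure and pharmacy sheets. For the 480 mg clause, Section 5 names 5.1 as the place for dosing details, and 5.1, Table 1 and Table 7 agree with one another, so a careful reader would treat the clause as a leftover. The dose counts above say how often nivolumab is scheduled, not how often anything would go wrong.

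Most of this stands, and it is why the point is minor. It does not make either statement right. Section 5.1 contradicts 8.2.7 without withdrawing it, and nothing else in the protocol corrects the strength. It also stands that the documents alone cannot settle the true strength: 10 mg/mL follows only if 100 mg/10 mL is correct.

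**Conclusion.** Both statements are wrong as written, and confidence is high. The two printed strengths differ by a factor of 2, and the 480 mg maintenance dose corresponds to zero scheduled doses. The severity is minor. The likely practical consequence is a pharmacy query, and no effect on the primary endpoint, sample size, analysis or secondary endpoints is claimed. The strength finding rests on arithmetic within one line. The maintenance finding rests on the agreement of 1.1, 2.4, 5, 5.1, 5.3.1 and Table 7 against a single clause. The volume illustration depends on assumed body weights, and the range of 31 to 47 doses assumes that every non-responder completes re-induction.

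**What to change.** - **8.2.2:** check the supplied vial label and print one consistent strength, which is 10 mg/mL if 100 mg/10 mL is right.
- **8.2.7:** delete the clause on 480 mg maintenance nivolumab. For clarity, describe weight-based dosing and weighing as applying to re-induction cycles 1-4.
- **Sites:** notify site pharmacies by memo or short amendment.

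The cost is one corrected figure, one deleted clause and a small clarification. Sample size, endpoints, data collection and analysis do not change.

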# 8.2.3 Storage and Stability

Nivolumab should be stored under refrigeration at 2°C to 8°C (36°F to 46°F). Protect from light by storing in the original carton until time of use. Do not freeze or shake.

# 8.2.4 Compatibility

When both nivolumab and ipilimumab are to be administered on the same day, separate infusion bags and filters must be used for each infusion. Nivolumab is to be administered first. The nivolumab infusion must be promptly followed by a saline flush to clear the line of nivolumab before starting the ipilimumab infusion. The second infusion will always be ipilimumab and will

# 8.2.5 Handling

Qualified personnel, familiar with procedures that minimize undue exposure to themselves and the environment, should undertake the preparation, handling, and safe disposal of the chemotherapeutic agent in a self-contained and protective environment.

start no sooner than 30 minutes after completion of the nivolumab infusion.

The product storage manager should ensure that the study drug is stored in accordance with the environmental conditions (temperature, light, and humidity) as determined by the sponsor. If concerns regarding the quality or appearance of the study drug arise, do not dispense the study drug and contact the sponsor immediately.

Investigational product documentation must be maintained that includes all processes required to ensure drug is accurately administered. This includes documentation of drug storage, administration and, as applicable, storage temperatures, reconstitution, and use of required processes (eg, required diluents, administration sets).

Please refer to the current IB/pharmacy reference sheets for storage, handling and preparation instructions.

# 8.2.6 Availability

Nivolumab will be provided by BMS from investigational supply.

## 8.2.7 Preparation

Please refer to the current IB/pharmacy reference sheets for preparation instructions. Study product should be prepared and dispensed by an appropriately qualified and experienced member of the study staff (eg, physician, nurse, physician's assistant, practitioner, pharmacist, or medical assistant) as allowed by local, state, and institutional guidance. Only qualified personnel who are familiar with procedures that minimize undue exposure to them and to the environment should undertake the preparation, handling, and safe disposal of biologic agents.

During the first 4 cycles, dosing of nivolumab will be based on the patient's weight in kilograms (kgs), whereas maintenance nivolumab will be administered at a flat dose of 480 mg. All patients should be weighed within 3 days prior to dosing for cycles 1-4 to ensure they did not experience either a weight loss or gain >10% from the weight used for the last dose calculation. If the patient experienced either a weight loss or gain >10% compared to the weight used for the last dose calculation, the amount of study drug must be recalculated.

Vials are for single use only. Any unused portion of the solution must be discarded in a biohazard waste disposal container with final disposal according to accepted local and national standards of incineration.

## 8.2.8 Administration

Nivolumab is to be administered as a 30-minute infusion. When both study drugs are to be administered on the same day, separate infusion bags and filters must be used for each infusion. Nivolumab is to be administered first. The nivolumab infusion must be promptly followed by a saline flush to clear the line of nivolumab before starting the ipilimumab infusion. The second infusion will always be ipilimumab and will start no sooner than 30 minutes after completion of the nivolumab infusion.

# 8.2.9 Ordering

Nivolumab will be supplied by BMS. No patients or third-party payers will be charged. Use the Drug Supply Request Form provided to order nivolumab. For all inquiries regarding nivolumab supplies, please contact: [contact].

## 8.2.10 Accountability

The investigator, or a responsible party designated by the investigator, will maintain a careful record of the inventory and disposition of nivolumab using a drug accountability form that is compliant with local and federal guidelines.

Additionally, a designated study team member will complete drug accountability/reconciliation based on the participant actual drug return versus the anticipated drug return and document the findings according to local and federal regulations and guidance.

# 8.2.11 Destruction and Return

After full drug accountability and reconciliation, all unused nivolumab will be destroyed according to site procedures. Destruction will be documented in the Drug Accountability Record Form. If any study drug is lost or damaged, the disposition of the study drug should be documented.

# 9. BIOMARKER, CORRELATIVE, AND SPECIAL STUDIES

The biomarkers for the trial include measurements from tumor tissues and analyses of blood samples to explore molecular, cellular, and soluble markers that may be relevant to the mechanism of action of the drug(s) or response/resistance to the drug(s). The correlative studies are best described as ancillary. While the goal of the correlative studies is to provide supportive data for the clinical study, there may be circumstances when a decision is made to stop a collection, not perform, or discontinue an analysis due to practical reasons (e.g., inadequate sample number), issues related to the quality of the sample, or issues related to the assay that preclude analysis, etc). Therefore, depending on the results obtained during the study, sample collection/analysis may be omitted at the discretion of the PI.

A cheek swab/saliva sample will be collected prior to treatment. In addition, peripheral blood will be collected for research at baseline, and after 3, 6, 12, 24, and 48 weeks of therapy. In

addition, peripheral blood samples will be collected at the time of progression (when feasible). Analyses of these samples may include investigation of ctDNA, such as quantification of ctDNA at different timepoints and examination of changes in copy number abnormalities and relevant pathogenic genes.

When safely feasible, tumor biopsies (excisional or core needle) will be obtained at baseline, between day 14 and 21 of cycle 1 of therapy (optional), and at the time of progression (optional). An archival sample within 90 days and without intervening treatment is acceptable as the pretreatment biopsy assuming that the following provisions are met: 1) Priority: tumor containing formalin-fixed, paraffin-embedded (FFPE) tissue block; 2) Priority: if the tumor containing FFPE tissue block cannot be provided in total, sections from this block should be provided that are freshly cut and mounted on positively-charged glass slides (SuperFrost Plus are recommended). Preferably, 25 slides should be provided; if not possible, a minimum of 15 slides is required.

These may be obtained by excisional or core needle biopsy. Biopsies may be analyzed for tumor and microenvironmental expression of checkpoint markers and for immune architecture by a combination of immunohistochemistry and multiparameter spectral imaging. Ideally, 5-6 core needle biopsies will be collected.

Analysis of tumor samples may include interrogation of the TME using multiplex immunofluorescence (MIF) with a specific interest in the frequency and distribution of immune cells (CD4+ T cells, CD8+ T cells, Tregs, NK cells, tumor-associated macrophages) and relevant immune checkpoint pathways (CTLA-4/CD86, PD-1/PD-L1). Findings may be validated and explored further using multiplexed ion beam imaging (MIBI).

Banked biospecimens will be handled in a manner that protects each subject's privacy and confidentiality. Banked biospecimens will be assigned the subject's study identification code (ID) at the site. The data generated from these banked biospecimens will also be indexed by this ID. Biospecimens will be kept until destruction in facilities with access limited to authorized personnel, and biospecimen-derived data will be stored on password-protected computer systems. The key between the subject's ID and the subject's direct personally identifying information (eg. name, address) will be held at the study site. Biospecimens will be used only for the purposes described in the protocol and informed consent document; any other uses require additional ethical approval. Unless a time limitation is required by local regulations or ethical requirements, biospecimens will be stored for many years (no time limit) to allow for research in the future, including research conducted during the lengthy drug-development process and also postmarketing research. Subjects may withdraw their consent for the use of their banked biospecimens at any time by making a request to the investigator; in this case, any remaining biospecimens will be destroyed, but data already generated from the biospecimens will continue to be available to protect the integrity of existing analyses. Unless prohibited by local regulations or ethics committee decision, a 4-mL blood genomic banked biospecimen Prep D1 (dipotassium edetic acid [ethylenediaminetetraacetic acid] [K2EDTA] whole-blood collection optimized for DNA analysis) will be collected at the time specified in the Study Calendar section of the protocol to be retained for potential pharmacogenomic/genomic/biomarker analyses related to drug response and disease/condition under study. For example, putative safety biomarkers, drug-metabolizing enzyme genes, drug-transport protein genes, or genes thought to

be related to the mechanism of drug action may be examined. The primary purpose is to examine DNA; however, the biospecimen may also be used to study other molecules (eg, RNA,

Details of time points and sampling are provided in the Study Calendar. Reference the laboratory manual for specimen collection, processing, and shipment instructions.

In order to complete all the assessments on tumor materials and blood samples, the Principal Investigator will provide instructions and necessary supplies to the site, including shipping materials and prepaid mailers. The panel of biomarkers might be adjusted based on results from ongoing research and/or safety; therefore, each patient will also be asked whether any remaining tumor tissue and/or blood-derived samples can be stored at a central repository (until such time as these samples cannot support any further analysis) and can be used for future exploratory research on the drug(s) and / or disease-related aspects. Biomarker analyses may be conducted after the conclusion of this study and may be based on samples derived from multiple studies.

